5.6 Full PK Profile Analysis Set

The Full PK Profile Analysis Set includes subjects in the full PK/PD subgroup who receive at least one dose of IMP, have no major protocol deviations affecting the PK variables, and have a sufficient number of PK concentration measurements to estimate the main PK parameters: maximum observed plasma concentration (C_{max}) and time to maximum observed plasma concentration (t_{max}), and area under the plasma concentration-time curve for the dosing interval (AUC_{tau}) where applicable.

The criteria of Major protocol deviations affecting the PK variables will be defined in the protocol deviation document. The process to review major protocol deviations potential impact on PK parameters will be ongoing and the final Full PK Profile Analysis Set will be determined during data review meeting.

The Full PK Profile Analysis Set will be used for PK parameter analyses using an NCA approach. The detailed PK analysis methodology will be included in a separate PK analysis plan.

5.7 Sparse PK Sampling Analysis Set

The Sparse PK Sampling Analysis Set includes all subjects who receive at least one dose of IMP, have no major protocol deviations affecting the PK variables and have at least one valid plasma concentration.

The criteria of Major protocol deviations affecting the PK variables will be defined in the protocol deviation document. The process to review major protocol deviations potential impact on PK parameters will be ongoing and the final Sparse PK Sampling Analysis Set will be determined during data review meeting.

Where possible, PK profile will be assessed following PK modeling, for each subject within the Sparse PK Sampling Analysis Set. This analysis will be described in a separate data analysis plan and reported in a standalone report.

5.8 PD Analysis Set

The PD Analysis Set includes all subjects in full PK/PD subgroup who have a sufficient number of PD measurements.

5.9 PK/PD Relationships Set

The PK/PD Relationships Set includes all subjects who receive at least one dose of IMP, have at least one valid plasma triptorelin concentration and have at least one PD measurement (PD markers: E₂, FSH and LH).

The PK/PD Relationships Set will be used to describe, where possible, the relationships between plasma triptorelin concentration and PD markers (E₂, FSH and LH) according to the actual treatment received for each subject. This analysis will be described in a separate data analysis plan and reported in a standalone report.

Statistical Analysis Plan

Version: Final 3.1

Ipsen Pharma; Protocol No. D-CN-52014-220

Date of Issue: 13DEC2019

CCI

6 DATA HANDLING

6.1 Time points and Visit Windows

Day 1 is defined as the day of first dose of IMP treatment. Relative days after Day 1 are calculated as (assessment date – Day 1 date) + 1. Relative days prior to Day 1 are calculated as (assessment date – Day 1 date). The day prior to Day 1 is Day -1.

Unless specified otherwise, baseline is defined as the last available assessment prior to the first dose of IMP; if assessment time and/or drug taken time is not collected, the assessment performed on the same day as first dose of IMP will be considered as baseline; if assessment date is missing, the assessments at the scheduled visits of screening (Visit 1) and Day 1 or baseline (Visit 2) will be considered as pre-baseline visits in flag baseline.

By-visit analyses on data will be analysed according to the scheduled visits outlined in the protocol and/or eCRF (Week xx). No visit windows will be applied for summary and analysis.

If subject early discontinued study, the measured safety and efficacy variables at early discontinued visit are collected in “End of study/early withdrawal visit”. Then the early withdrawal visit of safety and efficacy endpoints (except PD sampling) will be re-mapped to the visits using the time windows in Table 1.

Table 1 Scheduled Visits and Time Window

Scheduled Visit at Study Site	Target Day of the Visit	Protocol Visit Window	Time Window to Re-map End of Study Visit or Early Withdrawal Visit
Baseline	Day 1	Day 1	Day 1
Week 4	Day 29	Target Day \pm 3 days	Day 26 – Day 53
Week 8	Day 57	Target Day \pm 3 days	Day 54 – Day 81
Week 12	Day 85	Target Day \pm 3 days	Day 82 – Day 109
Week 16	Day 113	Target Day \pm 3 days	Day 110 – Day 137
Week 20	Day 141	Target Day \pm 3 days	Day 138 – Day 165
Week 24	Day 169	Target Day \pm 3 days	Day 166 – Day 193
Week 28	Day 197	Target Day \pm 3 days	Day 194 – Day 221
Week 32	Day 225	Target Day \pm 3 days	Day 222 – Day 249
Week 36	Day 253	Target Day \pm 3 days	Day 250 – Day 277
End of study visit (Week 40)	Day 281 or within 15 days after menses recovery	Target Day \pm 3 days	\geq Day 278

Data from end of study visit or early termination assessments will be combined with data from scheduled visits in the by-visit analyses only if no scheduled visit data for the same parameters at that visit.

The “final visit” will be added after all scheduled visits in by-visit analyses on safety data including lab tests, ECG, vital signs, physical/pelvic examination and pelvic type B ultrasound scan. The final visit means the last available measurements at scheduled or unscheduled visits after first study dose during the study.

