3.3 Exploratory Efficacy Endpoints

The exploratory endpoints for this study include:

- Percentage of subjects castrated (as defined by both $E_2 \leq 184$ pmol/L (50 pg/mL) and $E_2 \leq 110$ pmol/L (30 pg/mL)) at Week 24.
- Change in endometriosis-associated pelvic pain (by 10cm VAS) at Weeks 16, 20 and 24 and the end of study visit compared to baseline.
- Concentrations of E_2 , FSH and LH at Week 24.
- The PK/PD relationship will be explored (PD markers: E_2 , FSH and LH) for triptorelin acetate PR 1-month formulation and triptorelin pamoate PR 3-month formulation.

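### SAP section 6.1 contradicts itself on whether completers' end of study visits are re-mapped by study day; one reading would leave only late or non-recovering women in the end of study pain row

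*SAP*

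**What the plan says.** All the conflicting text is in SAP section 6.1.

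**Text that leaves completers where they are.** By-visit analyses follow the scheduled visits, and "No visit windows will be applied for summary and analysis". The re-mapping rule opens with a condition, "If subject early discontinued study, the measured safety and efficacy variables at early discontinued visit are collected in" the combined end of study/early withdrawal page, and then directs that "the early withdrawal visit of safety and efficacy endpoints (except PD sampling) will be re-mapped to the visits using the time windows" of Table 1.

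**Text that reaches completers.** The last column of Table 1 is headed "Time Window to Re-map End of Study Visit or Early Withdrawal Visit". Its end of study row has a re-map window of Day 278 or later, although the target day in that row is "Day 281 or within 15 days after menses recovery". The sentence below the table reads: "Data from end of study visit or early termination assessments will be combined with data from scheduled visits in the by-visit analyses", with the limit "only if no scheduled visit data for the same parameters at that visit".

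**The endpoint concerned.** SAP section 3.3 lists change in pelvic pain "at Weeks 16, 20 and 24 and the end of study visit compared to baseline" as exploratory. Section 7.6.4 analyses it on the FAS with the repeated-measures model used for the secondary pain endpoint. Protocol section 5.2.4.4 ties the end of study visit to return of menses (within 15 days), with Week 40 as the latest point. Protocol section 7.3.2 schedules the VAS every four weeks to Week 24 and then only at the end of study visit.

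**The concern.** A programmer who works from Table 1 and the combining sentence could move completers' end of study visits by study day and still be following the SAP. Most values would then leave the row they were collected for if most women recover before Day 278.

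The women left in that row would be those with late or no return of menses. Time to menses recovery is itself a secondary endpoint, so the row would be selected on a post-randomisation outcome. It would no longer estimate pain at the end of study visit as the protocol defines that visit, whether or not the arms recover at the same speed. The model gives treatment effects by visit, so the visit label decides which estimate each score enters.

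**Working it through.** **Step 1: reproduce the Table 1 windows.** The rule is lower bound = target day − 3 and upper bound = next target day − 4. All ten post-baseline rows match. The five that matter here:

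| Row | Target | Window |
|---|---|---|
| Week 24 | 169 | 169 − 3 = 166 to 197 − 4 = 193 |
| Week 28 | 197 | 194 to 225 − 4 = 221 |
| Week 32 | 225 | 222 to 253 − 4 = 249 |
| Week 36 | 253 | 250 to 281 − 4 = 277 |
| End of study | 281 | 281 − 3 = 278, no upper limit |

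**Step 2: which recovery days can reach the end of study row.** If menses return on Day R, a compliant visit falls between Day R and Day R + 15. Reaching Day 278 needs R + 15 ≥ 278, so R ≥ 263. With R = 262 the latest compliant visit is Day 277, which is Week 36. With R from 263 to 277 the row depends on how soon she is seen. Women without recovery attend at Week 40 (Day 281 ± 3) and stay in the row.

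**Step 3: where a completer's VAS goes under each reading.**

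| Day of end of study visit | Prose reading | Table 1 and combining sentence |
|---|---|---|
| 166-193 | End of study | Week 24 only if the Week 24 VAS is missing; otherwise neither row |
| 194-221 | End of study | Week 28 |
| 222-249 | End of study | Week 32 |
| 250-277 | End of study | Week 36 |
| 278 or later | End of study | End of study |

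At Weeks 28, 32 and 36 no VAS is scheduled, so no scheduled value blocks the move. For example, recovery on Day 200 with a visit on Day 210 puts the score at Week 28.

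**Step 4: distance from the last planned dose.** The last planned injections are on Day 85 (3-month arm) and Day 141 (1-month arm). The Day 262 cut-off is 262 − 85 = 177 days and 262 − 141 = 121 days after them. The same calendar cut-off therefore falls at different times after the last dose in the two arms. This makes unequal selection possible but does not show it.

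**Step 5: illustrative size.** The documents give no recovery times, so the share s seen before Day 278 is an assumption. Taking 300 randomised and the planning dropout of 10%, completers = 300 × 0.90 = 270 over both arms. The number left in the row under the table reading is 270 × (1 − s):

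| s | Left in end of study row |
|---|---|
| 20% | 270 × 0.80 = 216 |
| 50% | 270 × 0.50 = 135 |
| 80% | 270 × 0.20 = 54 |
| 95% | 270 × 0.05 = 13.5, about 14 |

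Under the prose reading all 270 remain, whatever s is.

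**The case against.** The best defence is that the prose governs. The sentence on early discontinuation is the only one that directs use of the windows, and it agrees with the default of nominal visits. The column heading may simply echo the shared end of study/early withdrawal page. The target in the last row recognises visits triggered by recovery as end of study visits. The combining sentence can be read as gap-filling that takes nothing out of the end of study row. Much of this stands: the prose reading is coherent and may well be what was intended.

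It does not remove the conflict. The combining sentence names end of study data as an alternative to early termination data, so it is hard to read as covering withdrawals alone. The last row's target admits visits that its own window excludes.

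A reader might infer more than the documents support:

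- That the move is settled. It is not, because the prose says otherwise.
- That end of study scores flow into Week 24. They enter only where the scheduled Week 24 VAS is missing.
- That the arms are shown to be selected differently. No recovery times are given for either arm.
- That end of study vital signs are lost. Section 6.1 adds a final visit row holding the last available measurement, which covers vital signs and partly protects them. It is for safety data, so the VAS has no such backstop.

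**Conclusion.** Wrong as written, as an internal contradiction; minor in severity. SAP section 6.1 supports two derivations of the end of study pain row. Under the prose the effect is zero. Under Table 1 and the combining sentence the row is confined to women whose menses returned on Day 263 or later (for a compliant visit) or had not returned by Week 40. How many that excludes cannot be stated from the documents; the range in Step 5 rests on assumed shares and on the planning dropout rate.

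The endpoint is exploratory and reported with a confidence interval. The primary Week 12 oestradiol endpoint is not affected, because a completer's end of study visit comes after Week 24 and cannot fall in the Week 12 window of Days 82-109.

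**What to change.** In SAP section 6.1:

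1. State that Table 1 re-mapping and the combining rule apply only to the early withdrawal visits of subjects who discontinue the study.
2. Retitle the last column of Table 1 so that it names early withdrawal visits alone.
3. Correct the last row so that its Day 278 window applies only to early withdrawal visits and no longer conflicts with its target for visits after menses recovery.
4. Remove end of study visits from the combining sentence.
5. Add that every other subject's end of study visit is analysed under its nominal end of study label, whatever its study day.

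The cost is SAP wording and one derivation. No new data are needed.

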5.2.4.4 End of Study Visit or Early Withdrawal Visit

The end of study visit will be the first visit within 15 days after the first day of menses recovery, or at Week 40 (Day 281±3), whichever is earlier. Subjects who withdraw from the study early will also attend an end of study visit.

Subjects who participate in the study in compliance with the protocol for 24 weeks of study drug administration will be considered to have completed study treatment. Subjects who participate in the study in compliance with the protocol for the 24 weeks of study drug administration, and complete the follow up period, will be considered to have completed the study.

For subjects who complete the study, or for those who withdraw prematurely from the study, final evaluations will be performed on the last day the subject receives the study drug, or as soon as possible afterwards. Subjects with ongoing AEs or clinically significant laboratory test abnormalities (as determined by the investigator) will be monitored as described in Section 8.1.3 and Section 8.1.2.4, respectively.

The following procedures will be performed at the end of study visit:

- E₂, LH and FSH concentrations (only if the subject's menses does not recover before Week 40)

- VAS assessment
- Vital signs
- Review of AEs
- New or changed concomitant medications/therapies
- Review of menses recovery status and record the date of menses onset (if applicable)

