7.2 Secondary and Exploratory Efficacy Endpoints and Evaluations

Secondary and exploratory efficacy endpoints and evaluations are summarised in [Table 7](#).

Table 7 Secondary and Exploratory Efficacy Endpoints and Evaluations

Measure	Timepoint	Variable	Endpoint
E ₂ concentration	Baseline, Weeks 4, 8, 12 and 24	Castration rate (percentage of subjects with E ₂ below castration levels) E ₂ concentration	Secondary endpoints Percentage of subjects castrated (E ₂ ≤184 pmol/L or 50 pg/mL) at Weeks 4 and 8. Percentage of subjects castrated (E ₂ ≤110 pmol/L or 30 pg/mL) at Weeks 4, 8 and 12. E ₂ concentration at Weeks 4, 8 and 12. Exploratory endpoints Percentage of subjects castrated (E ₂ ≤184 pmol/L or 50 pg/mL) at Week 24. Percentage of subjects castrated (E ₂ ≤110 pmol/L or 30 pg/mL) at Week 24. E ₂ concentration at Week 24.
Endometriosis-associated pelvic pain (by 10 cm VAS)	Baseline, Weeks 4, 8, 12, 16, 20, 24 and end of study/early withdrawal	Change in endometriosis-associated pelvic pain	Secondary endpoint Change in endometriosis-associated pelvic pain (by 10 cm VAS) at Weeks 4, 8 and 12 compared to baseline. Exploratory endpoint Change in endometriosis-associated pelvic pain (by 10 cm VAS) at Weeks 16, 20, 24 and the end of study visit compared to baseline.
FSH and LH concentrations	Baseline, Weeks 4, 8, 12 and 24	FSH concentration LH concentration	Secondary endpoint FSH and LH concentrations at Weeks 4, 8 and 12. Exploratory endpoint FSH and LH concentrations at Week 24.
Menses recovery	Baseline, date of first observation of menstrual bleeding at Weeks 28, 32, 36 and end of study/early withdrawal	Time to menses recovery	Secondary endpoint Time to menses recovery.

E₂=oestradiol; FSH=follicle stimulating hormone; LH=luteinising hormone; VAS=visual analogue scale.

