2.3 Sample Size and Power

The sample size was estimated based on data from Ipsen Study E-28-52014-705. Assuming the percentage of subjects castrated at Week 12 of triptorelin acetate PR 1-month treatment is no less than 92%, a sample size of 133 subjects in each treatment group will have 85% power to demonstrate the noninferiority of

Statistical Analysis Plan

Version: Final 3.1

Ipsen Pharma; Protocol No. D-CN-52014-220

Date of Issue: 13DEC2019

CCI

triptorelin pamoate PR 3-month to the comparator, when the lower limit of the 95% confidence interval (CI) of the difference in percentage of subjects castrated at Week 12 between the treatment groups is $\geq -10\%$ and with a 0.025 one-sided type I error rate.

Assuming that the dropout rate will be around 10%, a sample size of 300 randomised subjects in total is planned for this study.

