6.2 Handling of Dropouts or Missing Data

No data imputation will be performed for missing efficacy and safety variables, except efficacy endpoints of percentage of subjects castrated. If E₂ measurement is missing, the last available E₂ measurement at post-baseline visits will be used in deriving subjects castrated.

For laboratory values or concentration data below the lower limit of quantification (LLOQ) like “<xxx” or “<=xxx”, or above the upper limit of quantification (ULOQ) like “>xxx” or “>=xxx”, LLOQ or ULOQ

Statistical Analysis Plan

Version: Final 3.1

Date of Issue: 13DEC2019

Ipsen Pharma; Protocol No. D-CN-52014-220

CCI

(xxx) will be used for calculation of descriptive statistics. The original laboratory values or concentration data (“<xxx”, “<=xxx”, “>xxx” or “>=xxx”) are presented in the listing.

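### SAP Table 1 places most between-visit early-withdrawal pain scores at a visit already attended, or at none, so they drop out of the Week 4 to Week 24 VAS analyses

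*SAP*

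**What the plan says.** SAP 6.1 states that safety and efficacy data from an early withdrawal visit, apart from PD sampling, "will be re-mapped to the visits using the time windows in Table 1". The last column of Table 1 gives Week 4 as Days 26-53, Week 8 as Days 54-81, Week 12 as Days 82-109, and so on; Week 24 (target Day 169) is "Day 166 – Day 193". Baseline is Day 1 only. Scheduled data take priority: withdrawal data "will be combined with data from scheduled visits in the by-visit analyses only if no scheduled visit data for the same parameters at that visit".

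A pain score is collected at that visit. Protocol 5.2.4.4 says "Subjects who withdraw from the study early will also attend an end of study visit" and lists VAS among its procedures. Protocol Table 7 gives the VAS time points as "Baseline, Weeks 4, 8, 12, 16, 20, 24 and end of study/early withdrawal".

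Two other rules could have recovered a displaced score, but neither covers VAS. The final-visit row "will be added after all scheduled visits in by-visit analyses on safety data including lab tests, ECG, vital signs" and other safety examinations. SAP 6.2 says "No data imputation will be performed for missing efficacy and safety variables, except efficacy endpoints of percentage of subjects castrated".

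**The concern.** A withdrawal visit usually comes after the last scheduled visit attended. Because each window stays open until the day before the next protocol visit window, the withdrawal visit falls in the window of the visit just attended. That visit already has a VAS, so the later score is set aside.

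For example, a woman attends Week 4 on Day 29 and withdraws on Day 53, four days before the Week 8 target. Her withdrawal score maps to Week 4, which is filled, and she contributes nothing at Week 8.

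This sits badly with what the scale measures. Protocol 7.3.2 and Appendix 1 ask for the worst pain over the preceding 4 weeks. Her Day 53 score covers Days 26-53. That shares 24 of 28 days with the Week 8 recall period (Days 30-57), but only 4 (Days 26-29) with the Week 4 period (Days 2-29).

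VAS change at Weeks 4, 8 and 12 is a secondary endpoint, analysed with a repeated-measures model (SAP 7.6.2). Weeks 16, 20 and 24 are exploratory. Such a model leans on the scores observed before a woman leaves, and protocol 3.6 names lack of efficacy as a possible reason for leaving. The score left out is the one closest to that decision, and it has already been collected. By-visit vital signs are displaced in the same way, although their final-visit row keeps the value.

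**Working it through.** **Inputs.** Target days 29, 57, 85, 113, 141, 169 and the windows (SAP Table 1); the ±3-day visit window (protocol Table 2, SAP Table 1); 300 randomised (SAP 2.3), with the planning statement "Assuming that the dropout rate will be around 10" per cent, so 300 × 0.10 = 30 women.

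**1. Reproduce the windows.** Each bounded post-baseline window equals (target − 3) to (next target − 4). Week 4: 29 − 3 = 26 and 57 − 4 = 53. Week 24: 169 − 3 = 166 and 197 − 4 = 193. All nine rows from Week 4 to Week 36 agree. Each has 28 days, of which 21 (75%) fall after the visit's own ±3-day window. Days 2-25 (24 days) belong to no window.

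**2. Strict count.** Assume every scheduled visit is attended on its target day and the withdrawal visit is equally likely on any other day from Day 2 to Day 168. That is 167 − 5 target days = 162 days.

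| Outcome | SAP windows | Midpoint windows |
|---|---|---|
| Kept (before the target of its window) | 6 × 3 = 18 (11%) | 6 × 14 = 84 (52%) |
| Maps to an attended visit | 5 × 24 = 120 | 5 × 13 = 65 |
| No window | 24 | 13 |
| Not used | 144/162 (89%) | 78/162 (48%) |

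**3. Lenient count.** Count every day within ±3 of a target as usable, since the withdrawal visit might stand in for the scheduled one. Over Days 2-165 (164 days), the SAP windows give 5 × 7 = 35 usable, 5 × 21 = 105 mapped to an attended visit and 24 unmapped. The loss is 129/164 = 78.7%. Midpoint windows give 101 usable, so they lose 63/164 = 38.4%.

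**4. In women.** If all 30 planned dropouts leave on treatment and attend the visit, the SAP windows lose about 30 × 0.787 = 24 to 30 × 0.889 = 27 scores. On the strict count, scores kept are 30 × 18/162 = 3.3 under the SAP and 30 × 84/162 = 15.6 under midpoint windows.

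**5. Secondary endpoint only.** Before Week 12 (Days 2-84, less two target days) there are 81 days, so 30 × 81/162 = 15 women. The SAP keeps 15 × 9/81 = 1.7 scores; midpoint windows keep 15 × 42/81 = 7.8. The gain is about 6 scores over two arms and three visits.

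**The case against.** Several points on the other side have force.

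- **Timing is assumed.** Nothing in the documents says that withdrawal visits are spread evenly between visits. Protocol 4.3 and 5.2.4.4 ask for final evaluations on the last dosing day or as soon as possible afterwards, and dosing takes place at scheduled visits. If that is followed to the day, the visit's own VAS exists and little is lost. A visit within 13 days after an attended one would be set aside under midpoint windows too. This stands: the percentages illustrate a mechanism and do not predict a count.
- **Some scores are kept.** A withdrawal visit that replaces a scheduled visit, or follows a missed one within its window, is used. This also stands.
- **Early scores reach back before dosing.** A score in the first weeks recalls pre-treatment pain, so leaving the earliest days unmapped is defensible. It does not justify the later windows.
- **Scheduled data should take priority.** Agreed. The fault lies in where the windows sit.

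A reader might also infer more than the documents support. The scores do not vanish: SAP 7.1 lists all data. It is also unclear whether a withdrawal score could enter the exploratory end-of-study VAS endpoint, because the Table 1 column heading names both visit types while the text re-maps only early withdrawal visits. The SAP states no purpose for the re-mapping, so it cannot be said to work against its own purpose. Nor do the documents show that the VAS treatment difference is biased: no withdrawal pattern by arm is given, and no bias can be calculated.

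**Conclusion.** The mechanism is certain from SAP 6.1. A VAS taken between visits at early withdrawal normally maps to a filled visit or to none, and neither the final-visit row nor imputation brings it into the Week 4-24 analyses. How many scores this affects depends on timing that the documents do not give. Even spread gives a loss of 79% (lenient count) to 89% (strict count) of withdrawal days. The figures in women also need all 30 dropouts to leave on treatment and attend.

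The consequence is modest. It concerns secondary and exploratory VAS and by-visit vital signs. VAS is reported with confidence intervals and no success criterion, and the gain at Weeks 4-12 is about 6 scores. It would be wrong to read this as a threat to the non-inferiority conclusion, which rests on E2 at Week 12 with its own missing-data rule in SAP 6.2.

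**What to change.** In SAP Table 1, for early withdrawal visits during treatment, use midpoint windows for VAS and by-visit vital signs:

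- Week 4: Days 15-42
- Week 8: Days 43-70
- Week 12: Days 71-98
- Week 16: Days 99-126
- Week 20: Days 127-154
- Week 24: Days 155-182

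Keep the priority of scheduled data, and state that Days 2-14 stay unmapped. Do not apply these windows to E2 or to the primary endpoint.

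Do not add a rule that moves a displaced score to the next scheduled visit. It would keep 84 + 65 = 149 of 162 days (92%), but it could label a Day 30 score as Week 8, 57 − 30 = 27 days early. That is close to carrying the Week 4 value forward, which SAP 6.2 rules out for VAS.

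The cost is one table column and one sentence, with no new data. The downside is that a score may be labelled up to 14 days before its nominal visit (Day 15 as Week 4, target Day 29); the present windows allow up to 24 days after. For Days 15-28 part of the 4-week recall is pre-treatment: at Day 15, 28 − 15 = 13 of the 28 days. If the database is already locked, which the documents do not say, run the midpoint version as a labelled sensitivity analysis.
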